6.1 Outcome definitions/Analysis plan/Power calculation

Assess the feasibility of the RCT protocol by (a) calculating recruitment rate and participant retention, and (b) measuring the ability of Vitamin D administration to generate sustained increases in whole-blood Vitamin D concentrations (assessed 3 months after MVC).

Outcome definitions for Feasibility will be determined by the ability of the study team to: recruit 90 patients into the trial over the 15-month recruitment period, retain >80% of participants through 3-month follow-up, and achieve Vitamin D levels >20 ng/ml in 90% of treatment group at 3-month follow-up. In addition, will determine whether Vitamin D

administration per protocol can raise Vitamin D concentration in treatment group > 10ng/ml above baseline.

Analyses: Feasibility analyses will be performed using descriptive statistics. To assess Vitamin D increase according to treatment group, paired t-test will be used.

Power: Based on our previous Vitamin D trial and other work,⁴⁰⁻⁴⁵ we estimate that observed follow-up will be ~80%. With n=90 sample, this will permit follow-up rates estimates at 3 months with 95% CI $\pm 8.3\%$. This will permit assessment of follow-up feasibility and necessary sample size for an R01 RCT, if pilot results warrant. In addition, based on our previous Vitamin D trial, assuming 80% retention and Vitamin D concentration standard deviation of 4ng/ml, we will have >99% power to detect a change of 10 ng/ml in Vitamin D level in the treatment group.

Assess **preliminary efficacy** of Vitamin D administration per protocol to (a) decrease overall MSP severity during the 3 months following MVC, and (b) reduce MSP outcome disparity between Blacks vs. Whites following MVC.

Outcome Definitions for Pain Reduction between treatment groups will be assessed using patient-reported overall MSP scores (0-10 NRS) obtained at the ED, 3-week, 6-week, and 3-month assessments. NRS scores are valid measures of pain assessment.^{46,47}

Analysis plan Overall efficacy (a) will be addressed by evaluating for evidence that Vitamin D administration per protocol vs. placebo decreases overall MSP scores across study timepoints. The effect of the intervention on overall pain over time will be assessed by evaluating the coefficient for treatment group (β_1) in the model: $P_{ij} = \beta_0 + \alpha_{0i} + \beta_1 \text{Treatment}_i + \beta_2 \text{Race}_i + \beta_3 (\text{Treatment} \times \text{Race}) + \varepsilon_{ij}$, where P_{ij} is the pain score for the i th individual at time point j , β 's denotes fixed effects, α_{0i} is the random intercept for the i th individual and ε corresponds to random errors. Narrowing of racial disparity will be addressed by evaluating the interaction between race and treatment (β_3 in model above). Specifically, as described above we will assess whether Vitamin D has greater effect on pain outcomes over time in Blacks than Whites. All analyses will be evaluated on the basis of intention to treat. Prior to

[figure not shown]

Figure 2. Plot demonstrating power to detect a main effect (β_1 , black lines) and interaction (β_3 , blue lines) across a range of sample sizes, at three effect sizes estimated using simulation data generated from previous studies. Vertical red line indicates sample size proposed here (n=90). This demonstrates the power to assess Aim 2a (black) and 2b (blue).

data un-blinding, the study statistician will perform a blind review of the data in which statistical models will be developed and tested using dummy (computer-generated) treatment assignments. This is to ensure important covariates are added to the model prior to un-blinding to eliminate any bias of model covariate selection on results. After un-blinding the data, we will use appropriately specified linear contrasts of model parameters to estimate mean differences between participants treated with Vitamin D and placebo and 95% confidence intervals.

Power Estimates of power were derived using a Monte Carlo simulation based on parameter estimates from our observational data of MVC survivors using R (v. 4.0.2⁴⁸); and the *simr* package (v. 1.0.5⁴⁹). The power across a range of effect sizes for the main effect (a) is shown in Figure 2. These data and analysis must be seen as general estimates given that we lack intervention data for this population/condition.

Secondary Analyses:

Similar models as for the primary outcome will be fit for both the Brief Pain Inventory and the SF-12 Mental and Physical Component Scale Scores.

Sex as a biological variable (SABV) will be examined in treatment response including sex-by treatment interaction terms in the mixed effect model specified above and exploring sex differences in therapeutic response to Vitamin D and n-3 PUFAs.

General mental and physical health will be assessed using SF-12 physical and mental component scores (PCS and MCS) and the impact on physical and mental functioning will be determined in each of the treatment groups. A clinically important reduction in SF-12 PCS and MCS ranges between 2.5-4.5⁵⁰; therefore, a reduction of ≥ 4.5 will be considered a clinically significant improvement MCS/PCS.

Brief Pain Inventory: We will also use multivariable analysis to determine the role of n-3 PUFA/Vitamin D supplementation in pain interference using composite and individual measures of the Brief Pain Inventory.

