Objectives	Assess the feasibility of administering a single dose of Vitamin D in the emergency department to Blacks and Whites presenting within 24 hours of MVC with moderate or severe musculoskeletal pain (MSP), along with the ability of this dose to achieve sustained increases in Vitamin D levels. Evaluate the potential efficacy of this intervention to improve MSP outcomes in Blacks and to reduce MSP disparities in Black vs. White MVC survivors.
Number of Subjects	90
Diagnosis and Main Inclusion Criteria	Presentation to emergency department (ED) within 24 hours of motor vehicle collision with an initial moderate/severe MSP severity (0-10 NRS of ≥ 4)
Study Product, Dose, Route, Regimen	Ergocalciferol (Vitamin D2), 300,000 IU (2-150,000 IU capsules) orally administered once as a single dose prior to discharge from emergency department
Duration of administration	One-time dose
Reference therapy	Matched placebo to Vitamin D preparation

Statistical Methodology	Assess the feasibility of the RCT protocol by (a) calculating recruitment rate and participant retention, and (b) measuring the ability of Vitamin D administration to generate sustained increases in whole-blood Vitamin D concentrations (assessed 3 months after MVC). Assess for preliminary efficacy that Vitamin D administration per protocol (a) decreases overall MSP severity in Black Americans during the 3 months following MVC, and (b) reduced MSP outcome disparities between Black vs. White Americans following MVC.
-------------------------	---

Introduction

This document is a protocol for a human research study. This study is to be conducted according to US and international standards of Good Clinical Practice (FDA Title 21 part 312 and International Conference on Harmonization guidelines), applicable government regulations and Institutional research policies and procedures.

The main objective of this study is to determine whether administration of a single dose of Vitamin D in the Emergency Department following a motor vehicle collision reduces racial disparities in chronic pain following a traumatic event. This phase II, multicenter, randomized controlled trial is a pilot study to determine feasibility and potential efficacy (effect size, sample variation, response to study drug, ability to reduce racial disparity in pain outcomes) that can be used to adequately power a larger randomized controlled trial to fully assess efficacy.

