1.4 Dose Rationale and Risk/Benefits

The dose of Ergocalciferol that we propose, 300,000 IU, has been shown to effectively raise Vitamin D concentration by ~9 ng/ml, and to raise serum 25 hydroxyvitamin D concentration above 30 ng/ml (Vitamin D sufficient levels) for over 3 months⁵. The ability of our single-dose protocol to raise Vitamin D will be a primary feasibility endpoint of this pilot study. Importantly, this dose is extremely well-tolerated: in previous trials, reports of side effects/adverse events is rare,⁶ many studies administering single, high-dose regimens report no side effects⁷⁻⁹, and the most common side effects have been mild GI complaints (e.g. nausea).⁶ Vitamin D administration has also been demonstrated to be safe, even among individuals who are already Vitamin D sufficient. ¹⁰⁻¹² Based on the Code of Federal Regulation (CFR), Ergocalciferol will be exempt from an investigational new drug (IND) application.^{5,13-16}

Chronic pain is associated with reduced mental and physical health and interferes with essential activities of daily life. Currently there are limited treatment options to address chronic pain once it has become established and the overarching aim of this clinical trial is to prevent chronic pain development, therefore there is a critical unmet need of safe, non-addictive, non-invasive preventative treatment options that can be administered to MVC survivors in the aftermath of an injury. This study has the potential to benefit participants and future MVC survivors and improve pain and general health outcomes. The risks of taking Vitamin D are small. Side effects from Vitamin D are rare, however, it is possible that over supplementation of Vitamin D may be associated with headache, loss of appetite, dry mouth, metallic taste, and nausea/vomiting.

The risks to the subjects in experiencing these side effects are balanced against the potential for a new, safe, non-opioid preventative treatment option for chronic pain following MVC.

Study Objectives

2.1 Primary Objective:

1. Assess the feasibility of the RCT protocol by (a) calculating recruitment rate and participant retention, and (b) measuring the ability of Vitamin D administration to generate sustained increases in whole-blood Vitamin D concentrations (assessed 3 months after MVC).

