3.2 Study Overview

Described the sequence of events in recruiting 90 patients in a multi-center randomized controlled trial. To assess a key primary outcome, we will enroll 50% white and 50% black MVC into the study. Each participant will be screened in based on a point of care Vitamin D test. This will be performed at the time of screening. Individuals with a Vitamin D level <100 ng/ml will be enrolled. Patients will be randomized 1:1 to receive a single dose of 300,000 IU of ergocalciferol versus placebo and followed for 3 months. At 3 months, patients will send a blood sample easily collected at home on a blood spot card to assess Vitamin D level 3 months following injury which is a key feasibility primary outcome.

Patients presenting to the ED within 24 hours of MVC (n=90, 45 non-Hispanic Black, and 45 non-Hispanic White) will receive a single dose of study drug prior to ED discharge (1:1 allocation 300,000 IU ergocalciferol or placebo). Prior to study drug administration, a baseline assessment will be performed (see below), and a fingerstick blood sample will be obtained to evaluate 25-hydroxyvitamin D level. Online survey follow-ups assessing primary and secondary outcomes and potential adverse events will be performed 3 weeks, 6 weeks, and 3 months after ED enrollment by study RAs using web-based REDCap™ software. Participants will also complete brief “flash-surveys” at the 2-week, 4-week, and 5-week timepoints using REDCap survey links. At 3 months, participants will also perform a fingerstick blood collection at home and mail the sample in a prepaid envelope to a lab to be processed to enable assessment of 3 month 25-hydroxyvitamin D concentration by treatment group.

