3.4 Primary Study Endpoints

The primary endpoint of this study will examine the feasibility and efficacy of Vitamin D to improve overall MSP severity outcomes following motor vehicle collision in Blacks and Whites, as well as to reduce MSP outcome disparity between Blacks vs. Whites following MVC.

Outcome to assess feasibility: 90 patients will be enrolled, randomized into one of 2 treatment arms in a 1:1 ratio, and treated with study drug as a single-dose following motor vehicle collision with moderate to severe MSP within a 15-month period. Feasibility will also be measured by the ability to retain >80% of participants through 3-month follow-up, and achieve Vitamin D levels >20 ng/ml in 90% of treatment group at 3-month follow-up. In addition, will determine whether Vitamin D administration per protocol can raise Vitamin D concentration in treatment group >10 ng/ml above baseline. The concentration of Vitamin

D will be calculated before and after the treatment in each treatment arm to assess the response.

Outcome to assess efficacy: Efficacy of Vitamin D will be measured by difference in pain severity in treatment arms versus control arms. Pain reduction between treatment groups will be assessed using patient-reported overall MSP scores (0-10 NRS) obtained at the ED, 3-week, 6-week, and 3-month assessments. Estimates of efficacy will be obtained via repeated measures analysis using mixed effects models. Secondary Study Endpoints

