5.1 Enrollment Procedures

This first visit will take place upon admission to the hospital following MVC within 24 hours of the collision. Patients who meet inclusion criteria/exclusion criteria based on a review of the electronic medical record by research assistants, participants will be approached for participation. If the patient is interested in participating, they will then undergo informed consent. At this point in time, the participants will undergo baseline assessments (administered through REDCap) and collections of point of care Vitamin D levels with blood spot card. The participants will also have the option to consent to collect additional blood during a standard of care procedure while in the ED. The study would collect an EDTA tube,

a sodium heparin tube, and PAX gene RNA and DNA tubes. Patients with a Vitamin D level <100 ng/ml, will then take the baseline questionnaire. After all baseline data is collected, participants will be randomized and then administered appropriate study medication (Vitamin D or placebo). This administration will be documented in the MAR. Patients will be given a paper copy of their consent. Upon discharge of the patient, the patient will be given supplies to perform a home fingerstick blood draw (similar to one collected in the ED for baseline) and blotting on a blood spot card, which will occur at the 3-month timepoint.

Medical record information abstracted at time of admission will include information related to patient past medical history and initial motor vehicle collision care, and medication use prior to admission and prior to enrollment. Laboratory values relevant to patient renal and hepatic function will also be recorded (if obtained) along with any toxicology labs obtained by the primary treating team.

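### The vitamin D rise is a primary feasibility endpoint, but its only named test is a within-arm paired t-test; no vitamin D minus placebo difference with an interval is specified

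*Combined protocol and SAP*

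**What the plan says.** Section 1.4 (and 1.2 in the same terms) states: "The ability of our single-dose protocol to raise Vitamin D will be a primary feasibility endpoint of this pilot study". Section 3.2 also treats the 3-month level as a key primary feasibility outcome. Section 6.1 gives the aim as "measuring the ability of Vitamin D administration to generate sustained increases in whole-blood Vitamin D concentrations", which is a claim about what the drug does.

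For the analysis, 6.1 offers descriptive statistics for feasibility in general, and one test for vitamin D: "To assess Vitamin D increase according to treatment group, paired t-test will be used". The two numerical criteria in 3.4 and 6.1 both concern the treatment group alone: a 3-month level above 20 ng/ml in 90% of that group and, as an additional question, a rise of more than 10 ng/ml above baseline. The power statement in 6.1 also concerns the treatment group alone.

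Two other places mention both arms. Section 3.4 says that the concentration of vitamin "D will be calculated before and after the treatment in each treatment arm to assess the response". Section 3.2 says that the home blood sample is collected "to enable assessment of 3 month 25-hydroxyvitamin D concentration by treatment group". Neither names a between-arm estimate, test or interval.

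The one between-arm contrast with 95% intervals is in the efficacy part of 6.1: "we will use appropriately specified linear contrasts of model parameters to estimate mean differences between participants treated with Vitamin D and placebo". It is taken from a mixed model whose outcome is the pain score.

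**The concern.** The endpoint asks whether giving vitamin D raises the level. A paired test answers whether the level changed between the ED visit and 3 months in the people who received it. The two answers agree only if nothing else moves the level over those 3 months. Anything common to both arms, such as season, diet, recovery, own use of supplements or a difference between ED and home sampling, enters the within-arm change and is credited to the drug.

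The trial already has the remedy. It randomises a placebo arm, and the 3-month blood spot is planned for all participants. The plan simply does not specify an analysis of vitamin D level that uses this control.

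At stake is the quality of what the pilot hands on. The Introduction lists what it is to supply for a larger trial, including "effect size, sample variation, response to study drug". The response attributable to the drug is the placebo-corrected rise with its uncertainty, and the planned test does not give that.

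**Working it through.** **Inputs from section 6.1 and section 3.4.** 90 participants, 1:1, so 45 per arm; 80% retention; SD of vitamin D concentration 4 ng/ml; change of 10 ng/ml.

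**Assumptions.** Two-sided alpha 0.05 (6.1 states none for this test). The SD of 4 is given for concentration. The SD of change is 4 × √(2(1 − ρ)), with ρ the correlation between baseline and 3 months: 4.0 at ρ = 0.5 and 5.66 at ρ = 0. An SD of 8 is an assumed high value. The documents give no background drift, so 1 and 2 ng/ml are assumed.

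**1. The plan's own figure.** n = 45 × 0.80 = 36. The paired t noncentrality is 10 / (4/√36) = 15 on 35 degrees of freedom, and power is above 99.9%. The stated >99% reproduces. It is power against no change.

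**2. What the paired test reacts to.** The smallest mean change that is significant is t(0.975, 35) × SD / √36 = 2.030 × SD / 6. That is 1.35 ng/ml at SD 4, 1.91 at SD 5.66 and 2.71 at SD 8.

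**3. Shared drift with no drug effect.** Chance that the paired test in one arm is significant (noncentral t, 35 df):

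| Assumed drift | SD 4 | SD 5.66 | SD 8 |
|---|---|---|---|
| 1 ng/ml | 31% | 18% | 11% |
| 2 ng/ml | 83% | 54% | 31% |

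A between-arm test stays at 5% two-sided in every cell, because the drift cancels.

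**4. The same drift against the plan's >10 ng/ml question, read as a group mean.** Worst case in the table: drift 2, SD 8. The standard error is 8/6 = 1.33, so z = (10 − 2)/1.33 = 6.0 and the probability is about 1 in a billion. Drift of this size does not pass that threshold.

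**5. What the between-arm difference would deliver, even without baseline adjustment.** The 95% half-width is t(0.975, 70) × SD × √(2/36) = 1.994 × SD × 0.2357:
- SD 4: ±1.9 ng/ml
- SD 5.66: ±2.7 ng/ml
- SD 8: ±3.8 ng/ml

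Power for a difference of 9 ng/ml, the rise cited for this dose in 1.4, at SD 8 (two-sample t):
- 36 returned cards per arm: 99.7%
- 30 per arm: 99.0%
- 25 per arm: 97.4%

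The lower counts matter because returning the card is a separate task from the survey and is paid separately (10.3), so card return could fall below survey retention.

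**The case against.** The strongest reply is that the plan does not declare success on a paired p-value. Its vitamin D criteria are treatment-group thresholds, and step 4 shows that a drift of 1 to 2 ng/ml would not meet the >10 ng/ml question as a group mean. This stands. A reader might infer from the 31% to 83% that the trial could easily pass its vitamin D criterion with an inert drug. The documents do not support that: those figures describe the named test, and they rest on an assumed drift.

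A second reply is that the gap is partly covered. Levels are to be calculated in each arm and described, so a reader given means, SDs and counts by arm could form an unadjusted difference. This also stands. The data are planned; what is missing is the pre-specified estimate and interval. The words in 6.1 about treatment group may hint at a comparison, but a paired t-test cannot compare two independent arms. Nor does the plan say that it will set one arm's p-value against the other's to infer a drug effect, so error rates for that practice should not be charged to it.

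A third reply is that the larger trial will be sized mainly on pain and retention. That is fair. The placebo-corrected rise is useful to that design without being indispensable.

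Finally, a reader might see a contradiction between the >10 ng/ml question and the roughly 9 ng/ml cited for this dose. The documents do not establish one. The power sentence using 10 refers to the team's previous vitamin D trial, and Table 1 spans 6 to 13 ng/ml across doses and populations.

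**Conclusion.** The point holds as a gap in the specified analysis and is worth correcting. For a primary feasibility endpoint worded as an effect of vitamin D administration, the only named test ignores the placebo arm, and no vitamin D minus placebo estimate or interval is specified anywhere. The stated >99% power is arithmetically right for the within-arm test.

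The core rests on the wording of the plan and needs no assumption. The size is illustrative: 31% to 83% false significance within an arm at SD 4, and 11% to 31% at an assumed SD of 8, for an assumed shared drift of 1 to 2 ng/ml. The actual drift is unknown and could be nil. The treatment-group thresholds are not shown to be at fault; the weakness lies in the test and in the estimate carried forward.

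**What to change.** In 6.1, with a matching sentence in 3.4, make the main vitamin D analysis the vitamin D minus placebo difference in 3-month 25-hydroxyvitamin D, adjusted for baseline level (ANCOVA), with a 95% confidence interval. Keep the paired within-arm changes and the treatment-group thresholds as descriptive feasibility results. A two-sample comparison of change would be acceptable but is usually less precise.

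Optional wording: label the >99% as power against no change, and say whether the >10 ng/ml rise refers to the group mean or to each participant.

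The cost is one model and a few sentences. It needs no new samples, visits or participants, and step 5 shows that the planned numbers support the contrast even with a high SD and some loss of cards.

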4.3 Method for Assigning Subjects to Treatment Groups

Once a potential subject has been successfully screened, does not meet any exclusion criteria, is willing to participate in the study, and signs informed consent, the participant will be randomized by the study site using a minimization algorithm stratified on race, sex, and pain score. Randomization of participants using minimization will be accomplished using a centralized, web-based, validated (compliant with FDA 21 CFR Part 11) service (randomize.net). In this algorithm, a new participant is sequentially assigned to a particular treatment group by taking into account the covariates of the current and previously randomized participants. To further optimize power in this small, pilot study to examine the effect of race, and achieve a main goal of this study, a 1:1 ratio of non-Hispanic Black and White Americans will be enrolled. Once enrollment reaches 45 in a given race strata (e.g., non-Hispanic Black), enrollment for that race will cease. All participants, investigators, study

personnel, and follow-up team members will be blinded to allocation and concealment will be maintained throughout the study. Only the investigational pharmacy and study statistician will be unblinded to the drug the participant is receiving. They will not reveal this to the patient care team, investigative team, or to the participant. Dosing schedule, route of administration, number of pills in each dose, and the appearance of the capsules will be identical among each group.

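### The primary pain model counts the pre-dose ED score as an outcome and has no visit terms, so the treatment effect is understated by about 25-30% and power is lost

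*Combined protocol and SAP*

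**What the plan says.** Sections 3.4 and 6.1 both give the pain outcome as "patient-reported overall MSP scores (0-10 NRS) obtained at the ED, 3-week, 6-week, and 3-month assessments". Section 3.4 adds that efficacy will be estimated from these scores by repeated-measures mixed models.

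The model in Section 6.1 has an intercept, a random intercept per participant, Treatment, Race and Treatment × Race. It has no visit term, no treatment-by-visit term and no baseline pain. Efficacy is read from β1: "The effect of the intervention on overall pain over time will be assessed by evaluating the coefficient for treatment group". The stated aim is to show that vitamin D "decreases overall MSP scores across study timepoints". The disparity question is read from β3: "we will assess whether Vitamin D has greater effect on pain outcomes over time in Blacks than Whites".

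On timing, Section 3.2 states: "Prior to study drug administration, a baseline assessment will be performed". Section 5.1 states: "After all baseline data is collected, participants will be randomized and then administered appropriate study medication".

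Section 4.3 allocates treatment "using a minimization algorithm stratified on race, sex, and pain score". Neither sex nor pain score appears in the primary model.

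**The concern.** The ED score is measured before the participant is randomised or dosed, and minimisation on pain score holds the arms close together at that visit. Averaging it into the treatment coefficient pulls β1 and β3 toward zero by construction.

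The absence of a visit term does separate harm. Every participant enters with NRS of at least 4, and pain should fall afterwards. With no visit term that recovery goes into residual error. If one arm loses more participants, its mix of early high scores and late low scores changes, and a difference appears even when the drug does nothing.

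The Introduction says this pilot exists partly to supply an effect size and variation for powering a larger trial. An effect understated by 25-30%, used at face value, would inflate that trial's sample size by 1/0.75² = 1.8 to 1/0.70² = 2.0 times, other things equal. It could also discourage the trial altogether.

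**Working it through.** **The plan's own figures.** Power for the pain model appears only in Figure 2, which is not available, and the text gives no effect size, SD or correlation, so it cannot be reproduced. The other two figures in Section 6.1 do reproduce: 1.96 × √(0.8 × 0.2 / 90) = 8.3%, and a paired t-test with 45 × 0.8 = 36 pairs, SD 4 and change 10 has power above 99%.

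**Inputs from the documents.** Four outcome scores, one of them pre-dose; n = 90, 1:1, so 45 per arm; about 80% follow-up at 3 months. The brief surveys at 2, 4 and 5 weeks also record pain but are not in the listed outcome, so they are not counted.

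**Step 1: dilution with complete data.** The treatment coefficient equals the arm difference in four-visit means:

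E(estimate) = (0 + d + d + d)/4 = 0.75d.

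No SD, correlation or effect size enters. The same holds within each race, so β3 is also multiplied by 0.75. If the effect builds up linearly (d/3, 2d/3, d), the estimate is (0 + 1/3 + 2/3 + 1)d/4 = 0.50 of the 3-month effect.

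**Step 2: dilution with missing follow-up.** Counting observations, the share that is pre-dose is:

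- 95/90/80% observed at the three follow-ups: 1/3.65 = 27%
- 90/85/80%: 1/3.55 = 28%
- 80/80/80%: 1/3.40 = 29%

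Fitting the random-intercept model to simulated data gives 28-30% with intermittent missingness, 30-31% with monotone dropout at 90/85/80%, and 32-35% if the 20% lost provide no follow-up at all.

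**Step 3: power, analytic.** Assumptions: SD 2.5 at every visit, equal correlation r, complete data, two-sided α = 0.05, d = 1.0. The variance factors are (1+3r)/4 for the planned model, (1+2r)/3 for follow-up only, and (1+2r)/3 − r² for follow-up with ED pain as covariate. At r = 0.5 the standard errors are 2.5 × √(2/45) × √factor = 0.417, 0.430 and 0.340. The ratios of expected estimate to standard error are then 0.75/0.417 = 1.80, 1/0.430 = 2.32 and 1/0.340 = 2.94.

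| r | Planned | Follow-up only | Follow-up + ED covariate |
|---|---|---|---|
| 0.3 | 54% | 74% | 81% |
| 0.5 | 44% | 64% | 84% |
| 0.7 | 37% | 56% | 93% |

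**Step 4: power, simulated.** Assumptions: n = 90, mean NRS 7/5/4.5/4, ED NRS at least 4, 20% dropout, true effect −1.0, race-averaged contrast, 1,500 trials per scenario.

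| Between / residual SD | Planned model | Post-dose scores, visit and ED pain as covariates |
|---|---|---|
| 1.8 / 1.6 | −0.71, power 47% | −1.01, power 82% |
| 1.5 / 2.2 | power 49% | power 69% |

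A 600-trial repeat of the first row shows where the gain arises: planned model 45%; planned model plus visit 46%; ED score removed from the outcome 64%; ED score then used as covariate 81%. A separate simulation (follow-up SD 2.5, ED SD 1.7, retention 90/85/80%) gives 38-49% for the planned model, 54-62% for follow-up only and 63-75% with the ED covariate.

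**Step 5: unequal dropout, no drug effect.** With 30% dropout on active and 10% on placebo, the planned model is biased by +0.16 NRS points. The corrected model is biased by about 0.

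**The case against.** - **Blind review.** Section 6.1 lets important covariates be added before unblinding, so ED pain and sex might enter then. But the plan names neither, and adding a covariate does not take the ED score out of the outcome. The linear contrasts it mentions do not help either, because no combination of β0 to β3 separates follow-up from ED.
- **Cause.** The missing visit term is not by itself what dilutes the coefficient. This stands: adding only a visit main effect leaves 25% dilution with complete data and hardly changes power. A repair has to remove the ED score from the outcome or let the treatment effect differ by visit.
- **Power attribution.** In the repeat run, 17 of the 36 points gained (64% to 81%) come from using ED pain as a covariate, not from ending the dilution. This stands. Against a plain follow-up-only model, the separate simulation in Step 4 puts the loss at about 9-17 points.
- **Which visits j covers.** The model statement does not list them. Sections 3.4 and 6.1 do, and both include the ED.
- **Figure 2.** If effect sizes were entered directly as β1, its power may already be on the diluted scale. The text does not say. Race coding is also unstated, and with 0/1 coding β1 would be the effect in one race only.
- **Dropout.** The 30%/10% split has no basis in the documents, and the bias moves the false-positive rate only to about 6%. It shows a vulnerability, not an expected result.
- **It is a pilot.** Efficacy is preliminary and the scores are stored by visit, so the right effect could be recovered later. But the specified estimate is the one the plan would report and carry forward.

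**Conclusion.** The concern holds. As written, β1 and β3 estimate 0.75 of a constant post-dose effect with complete data. That follows from the outcome definition and the model alone. At about 80% follow-up the shortfall is roughly 27-31% under ordinary dropout patterns, and up to 35% if those lost give no follow-up. It is measured against the mean follow-up effect and is larger against the 3-month effect if benefit accrues over time.

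The loss of power is real in direction, but its size rests on assumed SDs, correlations and a 1-point effect: about 9-17 points against a follow-up-only analysis in the separate simulation, and 20-35 points against the covariate-adjusted analysis in the two main simulated scenarios. The dropout bias arises only if loss differs between arms.

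**What to change.** In Section 6.1, and in the matching text of Section 3.4:

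1. Restrict the outcome to NRS at 3 weeks, 6 weeks and 3 months.
2. Fit fixed effects for treatment, race, treatment × race, categorical visit, ED pain score and sex, with the random intercept kept.
3. Name the average post-dose treatment difference as the efficacy estimate, and state the race coding so that it is clear which contrast is tested.
4. Re-run the simr power with this model, restate Figure 2, and give its effect sizes, SDs and correlation in the text.

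If the team prefers to keep the ED score in the outcome, the model needs visit, treatment-by-visit and treatment-by-visit-by-race terms, with contrasts over the follow-up visits only. A visit main effect alone is not enough.

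The cost is plan wording and one repeat of the power simulation, before unblinding. No new data or participants are needed.
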